Hypothesis: Prophylactic intramuscular promethazine does not decrease pruritus in post-partum females that received 100mcg intrathecal morphine.

Alternate Hypothesis: Prophylactic intramuscular promethazine does decrease pruritus in post-partum females that received 100mcg intrathecal morphine.

Pruritus will be quantified by the ItchyQuant Scale, developed and validated by CG Haydek as seen below.⁹

Secondary Analysis

- Promethazine does not increase sedation compared to placebo (RASS scale)
- Promethazine does not increase pain compared to placebo (DVPRS scale)
- Promethazine decreases nausea and vomiting (rated as none, mild, moderate, severe)

6. Research Plan:

Inclusion criteria:

1. Pregnant adult female patients of at least 18 years of age consenting to a cesarean birth;
2. Willing to consent to study.

Exclusion criteria:

1. Male patients;
2. Incarceration;
3. Inability to communicate with the investigators;
4. Allergies to any medications used in the study;
5. Possessing any contraindication to spinal anesthesia (lack of consent, elevated intracranial pressure, preexisting neurological disease, thrombocytopenia/coagulopathy, hypovolemia, infection at the site of the procedure);
6. Patients with an already prolonged QTc (>500 ms)
7. Any reason an investigator believes study participation would not be in the best interest of the potential subject.

DESIGN

STUDY PROCEDURES

Recruitment

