The patient will come to the obstetric (OB) pre-operative holding area where we will obtain her medical history, perform a physical exam and consent her for the cesarean delivery. The patient will have already spoken with a study coordinator and/or PI/Co-I more than one day prior to arrival regarding potential participation in the study. The patient will be approached by one of the study team members (anesthesiologists). We will review the consent form, explaining that itching is a common side effect of the intrathecal morphine and we are trialing a medication that would prevent the itching. If the patient agrees to participate, we will obtain signed consent, contact the study coordinator to be prepared for questionnaires post-procedure and then obtain a blinded syringe from pharmacy for the treatment. [name] will randomize the patient for the study to determine which medication the mother will receive using a stratified randomization design generated with MAPLE software.

The patient will then go back to the operating room when it is her operative time, and we will perform the spinal with bupivacaine, morphine and fentanyl, which is standard at our institution (see standard of care medications below). Once the spinal is confirmed to be adequate, the surgical team will be called in to perform the procedure. Once the baby is delivered and the procedure is completed, we will inject the blinded syringe of medication into the patient's left thigh since she will still be numb from the spinal. When the patient arrives to the PACU, we will assess the 4 variables 1 hour after medication is given in PACU and then between 4-5 hours post-op and at 24 hours post-op (+/- 2 hours). All evaluations will be done in person or by phone call from study coordinator.

If patients are still reporting pruritis that is not controlled, the rescue treatment will be butorphanol 1mg IV q3h, as this is the current regimen at our institution.

Treatment/Therapy

The treatment will consist of a blinded syringe of 1cc clear liquid (blinded to patient and physician – only pharmacist will know what it contains). This injection will be given in the left thigh after the cesarean delivery is completed.

Contents of syringe: (either)

- 1cc 0.9% Sodium Chloride (placebo)
- 1cc 25mg/ml Promethazine (study medication)

Extra studies/procedures required

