| Final Evaluation of variables (Phone call from coordinator) | | | | 24 h |

STATISTICAL METHODS, DATA ANALYSIS, AND INTERPRETATION:

Our plan is to recruit 50 patients for each arm of the study. With 50 patients on placebo and 50 patients on Phenergan, there will be a greater than 80% chance of detecting a significant difference of 20% or more at a two-sided 0.05 significance level. This assumes that severe itching occurs in 50% of patients and Phenergan reduces this proportion to 20%.

We will use Fisher's exact test to compare groups on severity of itching. We will also use Wilcoxon's rank sum test to compare groups on degree of itching as measured by the ITCHYQUANT. [name], the study biostatistician, will perform all statistical analyses.

DATA STORAGE AND DE-IDENTIFICATION PLANS:

The original, hard-copy signed informed consent forms and rhythm strips will be stored within the locked Anesthesiology research office and will remain with the Principal Investigator for at least 7 years. Data will be entered into an Excel spreadsheet kept on a password-protected and encrypted computer and retained by the Principal Investigator for at least 7 years.

Patients will be de-identified. No names, MRN's, or other identifying information will be stored in the spreadsheet. Pain, itching, sedation and nausea/vomiting will be collected at three intervals by a study coordinator and added to the de-identified spreadsheet. Age group, medical conditions such as diabetes and pre-eclampsia as well as BMI groups, will be used to determine confounders in the data. None of this collected information will be used to identify the patients.

7. Potential Risks:

Subjects will be given clear verbal and written instructions to contact [name] in the Department of Anesthesiology with questions or concerns regarding their study participation. If a patient experiences an injury that is directly caused by this study, they will receive professional medical care at the University of Florida. No other compensation is offered. Any adverse events will be reported to the

IRB using the standard adverse events reporting website and on continuing reviews (depending upon severity, as defined by the IRB).

1. Sedation (study variable). Promethazine can cause sedation which will be studied.
2. Concern for QT prolongation on the ECG causing cardiac arrhythmias. QTc evaluated on patient monitor, rhythm strip to be printed off and saved in research binder with QTc labeled clearly.

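### Itch is scored at three contacts and compared by two tests, but the plan names no primary test, no deciding time point or summary, and no multiplicity rule, so the stated alpha and power attach to no single comparison

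*Combined protocol and SAP*

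**What the plan says.** Section 5 (Specific Aims) sets one efficacy hypothesis: "Alternate Hypothesis: Prophylactic intramuscular promethazine does decrease pruritus in post-partum females that received 100mcg intrathecal morphine". It adds that "Pruritus will be quantified by the ItchyQuant Scale". Sedation, pain, and nausea and vomiting are listed there under secondary analysis. The Abstract gives the primary aim only as evaluating how effective the prophylaxis is.

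Section 6, under Patient typical day, sets the assessments: "we will assess the 4 variables 1 hour after medication is given in PACU and then between 4-5 hours post-op and at 24 hours". The Table of Study Events lists the same three contacts, and the data storage section confirms that "Pain, itching, sedation and nausea/vomiting will be collected at three intervals by a study coordinator".

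The statistical section of Section 6 states that with 50 patients per arm "there will be a greater than 80% chance of detecting a significant difference of 20% or more at a two-sided 0.05 significance level". It continues: "This assumes that severe itching occurs in 50% of patients and Phenergan reduces this proportion to 20" per cent. The analysis is then two sentences: Fisher's "exact test to compare groups on severity of itching", and also Wilcoxon's "rank sum test to compare groups on degree of itching as measured by the ITCHYQUANT".

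**The concern.** One hypothesis can be tested in at least six ways (two tests at each of three contacts), and in more if a summary such as severe itching at any contact is allowed. The plan does not say which result decides. Two consequences follow.

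- **Error rate.** The deciding comparison can be chosen after the data are seen, and nothing in the plan holds the overall error at the stated 5%.
- **Power.** The rates of 50% and 20% could mean severe itching at one contact, at each contact, or at any contact. Power depends on which, so the power statement cannot be interpreted even if nobody selects among results.

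**Working it through.** **Inputs from the protocol (Section 6).** 50 per arm; two-sided 0.05; severe itching 50% against 20%; Fisher's exact test and Wilcoxon's rank sum test; three contacts.

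**Inputs that are assumptions.** Itch as a 0-10 score; severe = 7 or more (8 or more in some runs); latent normal scores with within-patient correlation 0 to 0.9; the rate of severe itching at each contact. The documents give none of these in readable text.

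**1. The plan's own figure.** Power = sum over a, b of Bin(a; 50, 0.50) × Bin(b; 50, 0.20) × 1[Fisher p ≤ 0.05] = 0.853. Power above 80% is confirmed for one Fisher test to which these rates apply.

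**2. Error of one Fisher test.** The same sum with equal rates p in both arms:

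| p | 5% | 10% | 20% | 35% | 50% |
|---|---|---|---|---|---|
| exact error | 0.7% | 1.8% | 2.8% | 3.0% | 3.5% |

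For rates of 10-50% this is 2-4%: the test is conservative.

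**3. Fisher at three contacts, any positive counts.** With independent contacts the error is 1 − (1 − s1)(1 − s2)(1 − s3), where s is the error from step 2. Correlation was handled by simulation (20,000 to 40,000 trials per setting).

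| Severe rate at 1 h / 4-5 h / 24 h | Independent (formula) | Range, correlation 0 to 0.9 |
|---|---|---|
| 50 / 50 / 50% | 1 − (1 − 0.0352)³ = 10.2% | about 8-10% |
| 20 / 20 / 20% | 1 − (1 − 0.0282)³ = 8.2% | about 7-8% |
| 5 / 50 / 20% | 6.9% | 6.3-7.1% |
| 10 / 10 / 10% | 5.3% | 4.2-5.3% |
| 5 / 30 / 5% | 4.5% | 4.2-4.5% |
| 2 / 50 / 5% | 4.2% | 4.1-4.4% |
| 5 / 5 / 5% | 2.1% | 1.8-2.2% |

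**4. Both tests at three contacts, any positive counts.** By simulation with a tie-corrected Wilcoxon test, the error is about 11-19% when severe itch is common at all contacts. It is about 10-16% for the 2 / 50 / 5% pattern. Wilcoxon is little affected by how rare severe scores are, so this figure stays well above 5%. Both tests at a single contact give about 5-7%.

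**5. Power under different meanings of 50% and 20%.**

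- *Rates at any contact.* With independent contacts the rate per contact is 1 − 0.50^(1/3) = 20.6% against 1 − 0.80^(1/3) = 7.2%, and Fisher at one contact has 38% power. At correlation 0.9 the rates are about 40% and 14%, and power is 79%.
- *Rates at each contact.* With independent contacts, severe at any contact is 1 − 0.50³ = 87.5% against 1 − 0.80³ = 48.8%, with 99% power. At correlation 0.9 power is 90%.

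The same sample size therefore gives anything from 38% to 99% power, depending on a choice the plan leaves open.

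**The case against.** The strongest reply is that the plan does have a lead analysis. The sample size rests on the proportion with severe itching, Fisher is listed first, and Wilcoxon is added as a further test. On that reading Wilcoxon is supportive. This is the natural reading and it stands as far as it goes, but it settles only the test. It does not say which contact, or which summary of three contacts, the test is applied to.

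Second, the plan nowhere says that one positive result is enough. That is correct. A reader might infer from 10-19% that the trial runs at that error rate; the documents do not support this, because the figure needs a decision rule that they do not state. They also contain nothing to exclude it.

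Third, a reader might infer that Fisher at three contacts must exceed 5%. It need not. Nothing says that severe itching is equally common at each contact, and step 3 shows 4-5% when it is concentrated at one contact and about 2% when it is near 5% throughout.

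Fourth, a reader might conclude that severe is undefined. The scale figure is missing from the text available here and may show bands, so that cannot be claimed.

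Finally, the Background says that itching lasts 24-48 hours. It would be tempting to infer that promethazine's effect wears off before the last contact, but the documents give no duration of effect.

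**Conclusion.** The point holds as a missing definition of the primary comparison. No section names the deciding test, the time point or summary, or a multiplicity rule, and the planning rates carry no time. This is more than missing detail, because the main claim, its error rate and its power all depend on it.

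The inflated error is conditional on any positive result being allowed to carry the claim: about 10-19% with both tests at three contacts. With Fisher alone it is about 2-10%: 6-10% if severe itch is common (roughly 20-50%) at all or most contacts, and about 5% or less if it is rare or confined to one. If the team already intends a single Fisher test, the error is not inflated and power is 85%, provided that 50% against 20% refers to that comparison. The omission itself rests on the text alone; only the sizes depend on the assumptions listed in the working.

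**What to change.** Before unblinding, amend the statistical section of Section 6 to name one primary comparison at two-sided 0.05: Fisher's exact test on the proportion with severe itching. Apply it at the one time point, or to the one summary over the three contacts, to which the 50% and 20% refer, and say which that is. State the score that counts as severe unless the scale figure already gives it. Label Wilcoxon and the remaining time points secondary, so that they cannot carry the primary claim.

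This costs wording only; the sample size, the contacts and both tests stay. It is cheaper than splitting alpha: at 50% against 20%, Fisher's power falls to 72.9% at 0.05/3 and to 64.3% at 0.05/6.

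The price is that a clear result at another contact, or on Wilcoxon alone, can no longer support the claim. The choice between time point and summary also matters. Suppose the effect is present at the first two contacts (50% against 20%) and absent at 24 h (50% in both arms). With independent contacts, severe at any contact is then 87.5% against 1 − 0.8 × 0.8 × 0.5 = 68%, with 58% power; at correlation 0.9 power is about 15%. A single contact with the effect present has 85%. That loss of effect is an assumption. A single contact carries the opposite risk, 38-79% power, if the planning rates were meant for any contact.

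### Fisher's exact test is valid but conservative for severe itching; Boschloo's exact test keeps the 5% bound and gains some power at no cost in patients

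*Combined protocol and SAP*

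**What the plan says.** The relevant text is in section 6 (Research Plan) of the combined protocol and SAP, under Statistical Methods, Data Analysis, and Interpretation.

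- Size: "Our plan is to recruit 50 patients for each arm of the study".
- Power: "there will be a greater than 80% chance of detecting a significant difference of 20% or more", "at a two-sided 0.05 significance level". The rates assumed for severe itching are 50%, falling to 20% with promethazine.
- Analysis of severity: Fisher's "exact test to compare groups on severity of itching".
- A second itch analysis: Wilcoxon's "rank sum test to compare groups on degree of itching as measured by the ITCHYQUANT".

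The section does not say which test the power figure was based on. It does not mention that Fisher's test is conservative, gives no cut-off for severe itching, and names no effect estimate or confidence interval for itch.

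**The concern.** Fisher's test conditions on the total number of events. With two arms of equal size, few distinct tables are then possible for each total, and the p-value moves in coarse steps. The chance of a false positive therefore stays well below the nominal 5%, and part of the permitted error rate goes unused.

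What is at stake is power in a small trial. An observed 25/50 versus 15/50, which is a 20-point difference, gives p = 0.066 by Fisher and p = 0.044 by Boschloo's exact test. The result is non-significant under the planned test and significant under another exact test that also holds the error rate at or below 5%.

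**Working it through.** **Inputs, all from the statistical methods text.** n = 50 per arm; two-sided alpha = 0.05; severe itching 50% versus 20%; a binary outcome, as the power statement implies. The wording about a difference of 20% or more is also read as 50% versus 30%.

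**Step 1. The plan's own figure.** By the normal approximation, power = Φ{[d√n − 1.96√(2p̄(1−p̄))] / √(p1(1−p1) + p2(1−p2))}.

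- 50% v 20%: d = 0.30, p̄ = 0.35. (2.121 − 1.96 × 0.6745) / 0.6403 = 1.248, so power is 89.4%.
- 50% v 30%: d = 0.20, p̄ = 0.40. (1.414 − 1.96 × 0.6928) / 0.6782 = 0.083, so power is 53.3%.

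**Step 2. Exact calculation for Fisher.** Let R be the set of the 51 × 51 possible tables with two-sided Fisher p ≤ 0.05. Then power(p1, p2) = Σ over R of Bin(a; 50, p1) × Bin(b; 50, p2), and the true size at a common rate p is the same sum with p1 = p2 = p. Fisher's power is 85.3% at 50% v 20%, so the stated figure above 80% is reproduced with the planned test. It is 46.3% at 50% v 30%.

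**Step 3. Boschloo.** This test uses the Fisher p-value only to order the tables. It rejects when that p-value is at most c, where c is the largest value that keeps the true size at or below 0.05 for every common rate. At 50/50, c = 0.0693. Because 0.0693 exceeds 0.05, the region contains every Fisher rejection; it adds 56 tables.

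| Common rate | Fisher size | Boschloo size |
|---|---|---|
| 20% | 2.8% | 4.0% |
| 35% | 3.0% | 4.6% |
| 50% | 3.5% | 4.2% |
| Maximum over all rates | 3.5% | 4.9% |

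| True rates (50/50 arms) | Fisher power | Boschloo power | Gain, points (before rounding) |
|---|---|---|---|
| 50% v 20% | 85.3% | 88.8% | 3.6 |
| 50% v 25% | 67.5% | 73.8% | 6.3 |
| 50% v 30% | 46.3% | 53.2% | 6.9 |
| 60% v 40% | 46.2% | 48.7% | 2.5 |

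**Step 4. Unequal arms.** The same enumeration for other numbers analysed, with the ordering by the two-sided Fisher p-value:

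| Placebo/promethazine | Fisher maximum size | Gain at 50% v 20% | Gain at 50% v 30% |
|---|---|---|---|
| 49/50 | 4.4% | 2.1 | 1.8 |
| 51/49 | 4.6% | 1.8 | 1.1 |
| 50/48 | 4.2% | 1.5 | 1.2 |
| 47/50 | 4.2% | 0.9 | 1.0 |
| 48/52 | 4.4% | 2.0 | 1.4 |
| 48/47 | 4.0% | 2.9 | 4.5 |
| 50/47 | 4.2% | 4.1 | 5.1 |

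With unequal margins Fisher's p-value takes more distinct values, so less is lost. Fisher's size is at most 5% for any arm sizes, so c cannot fall below 0.05 and the gain cannot be negative. This argument needs Boschloo's ordering to be the same two-sided Fisher p-value. Some software instead doubles the one-sided Boschloo p-value. At 50/50 the two definitions give the same region, but at 51/49, 50/48 and 48/52 the doubled version does not contain every two-sided Fisher rejection.

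**The case against.** The strongest reply is that nothing in the plan is wrong. A 0.05 significance level is an upper bound, and Fisher's test respects it. A reader might infer from the sizes above that the trial runs at a different error rate from the one stated, or that its power claim fails under the planned test. The documents support neither: the bound is kept, and at the stated rates of 50% and 20% Fisher's power is 85.3%.

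A reader might also take a loss of 4 to 7 points as a general property of this trial. That range belongs to particular scenarios at exactly 50/50, and even there the gain is 2.5 points at 60% v 40%. Exact balance is not assured. Fifty per arm is a recruitment target, no block size is given for the stratified randomization, a QTc exclusion read from the intraoperative monitor may follow randomization, and outcomes are collected up to 24 hours. Nor should the size be described as about 2%: that needs a common rate near 11% to 12%, outside the plan's 20% to 50%.

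Two further points stand. The figures apply only to a two-category outcome, which the plan implies but does not define; they would not carry over to a table with several severity grades. The Wilcoxon test also means that this is not the only itch analysis.

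The argument that conditional versus unconditional testing is a matter of taste does not remove the point. Under the stated ordering, one rejection region contains the other and both keep the 5% bound, so the choice has a definite direction.

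**Conclusion.** The point holds as an efficiency improvement. With exactly 50 per arm and a binary endpoint, Fisher's true size is 2.8% to 3.5% at common rates of 20% to 50%. Boschloo's test uses more of the permitted 5% and gains 3.6 points at the design rates and 6.9 points at 50% v 30%. With slightly unequal arms the gain is usually 1 to 3 points, sometimes more, and never negative under the two-sided Fisher ordering.

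The change does not settle the mismatch between the 20-point difference in the power sentence and the 30-point difference in its assumed rates. At 50% v 30%, power is about 53% even with Boschloo's test. The absence of an effect estimate and interval for itch is a reporting detail that the same edit can cover.

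**What to change.** Before unblinding, replace the Fisher sentence with: *The proportion with severe itching will be compared by Boschloo's exact unconditional test, two-sided, alpha 0.05, and reported as a risk difference with 95% confidence interval.*

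In the same edit:

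- state that tables are ordered by the two-sided Fisher p-value, and name the software, so that the advantage over Fisher also holds with unequal arms;
- define severe itching as a yes/no outcome, since the test and the figures depend on it;
- keep Fisher's test as a sensitivity result;
- state power as about 89% for 50% v 20% at 50 per arm, and do not claim it for a 20-point difference.

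The cost is one or two sentences, with no extra patients or data, and the test is available in standard software. The downside is that readers know it less well than Fisher's, which the sensitivity result covers.

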It is standard of care for all patients for this surgery to have intraoperative 5 lead EKG monitoring. All study patients will have QTc evaluated on the anesthesia monitor. As part of the study, rhythm strips will be printed out and saved in study binder. Any patients with an already prolonged QTc (>500 ms) will be excluded from the study.

Recording data responsibilities

1. Anesthesia attending on OB for the day will consent patient if they agree to the study.
2. [name] team will perform randomization.
3. Study coordinator will be contacted once patient is enrolled.
4. Time 0 will be recorded by resident/attending in the room at the time the medication is given.
5. Study coordinator will contact patient in person or by phone at 1 hour, 4-5 hours , and 24 (+/- 2 hours) hours to assess given variables.

Drugs that will be given as STANDARD OF CARE during the study will be:

1: Bupivacaine 0.75% 1.4-2.0 IT (Spinal anesthetic)

2: Fentanyl 20 mcg IT (Spinal anesthetic)

3: Preservative Free Morphine 100 mcg IT (Spinal anesthetic)

4: Butorphanol 1mg IV every 3 hours (rescue treatment)

5: Nalbuphine 2.5mg IV every 6 hours as needed for itching

6: Ondansetron 4mg IV every 6 hours as needed for nausea

7: Ketorolac 30mg IV once

8: Acetaminophen 975mg by mouth every 6 hours (scheduled)

9: Phenylephrine 100-200mcg as needed every 2 min and phenylephrine infusion 0.1 mcg/kg/min IV titrated to maintain maternal BP within 20% of baseline.

10: Ephedrine 5-10mg IV as needed every 2 min to maintain maternal BP within 20% of baseline, secondary agent to phenylephrine bolus and infusion and/or if maternal HR falls below 70 bpm.

11: Cefazolin 2g IV once before incision

12: Azithromycin 500mg IV once before incision

13: Clonidine 15-30mcg IT (Spinal anesthetic)

If penicillin allergic (given as STANDARD OF CARE):

1: Clindamycin 900mg IV once before incision

2: Gentamicin 1.5mg/kg IV once before incision

Drugs that will be given as part of the study:

1: Intramuscular Promethazine 25mg (25mg/mL)
2: Intramuscular 0.9% Sodium Chloride (placebo, also 1mL)

Table of Study Events

| Activity | Time Point | Time Point | Time Point | Time Point |
|--|------------|------------|------------|------------|
| Injection of blinded medication | 0 | | | |
| First Evaluation of variables (Phone call from coordinator) | | 1 h | | |
| Second Evaluation of variables (Phone call from coordinator) | | | 4-5 h | |

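### QT prolongation is a named risk of the study drug, but the QTc strip has no stated time relative to the injection, serves only for exclusion, and no post-dose QTc reading, recording or summary by arm is specified

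*Combined protocol and SAP*

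**What the plan says.** **The risk and the response to it.** Item 2 of section 7 (Potential Risks) reads "Concern for QT prolongation on the ECG causing cardiac arrhythmias", and the response follows directly: "QTc evaluated on patient monitor, rhythm strip to be printed off and saved in research binder with QTc labeled clearly". No time is attached.

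**The reading.** In section 6, under the heading on extra studies and procedures, the setting is given as "It is standard of care for all patients for this surgery to have intraoperative 5 lead EKG monitoring", followed by "All study patients will have QTc evaluated on the anesthesia monitor". Strips are to be printed and kept in the study binder. The stated use is "Any patients with an already prolonged QTc (>500 ms) will be excluded from the study", which matches exclusion criterion 6.

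**The dose.** Under the patient's typical day, section 6 says "Once the baby is delivered and the procedure is completed, we will inject the blinded syringe of medication into the patient's left thigh". The list of data recording responsibilities defines Time 0 as the moment of that injection.

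**Follow-up.** The same account of the day says "we will assess the 4 variables 1 hour after medication is given in PACU and then between 4-5 hours post-op and at 24 hours". The data storage section names the variables as pain, itching, sedation and nausea/vomiting. Contacts may be in person or by phone; the Table of Study Events labels all three as phone calls.

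**Analysis and safety review.** The statistical section covers itching only. The Safety Endpoint text provides a general adverse event log, a team review if events exceed expectation, and an investigators' meeting after any major reaction.

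**The concern.** A measurement can serve as a safeguard against a drug effect only if it is made after the drug is given, at a known time, and is recorded where someone will look at it. The QTc strip is offered in section 7 as the response to the drug's QT risk. What section 6 describes is an eligibility screen. A screen can keep patients with an already long QTc out of the trial, but it carries no information on what the injection does to the QTc of those who stay in.

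What is at stake is safety information, not the efficacy result. The Safety Endpoint review depends on events being noticed and logged. QTc prolongation without symptoms would not be noticed unless someone reads a strip after dosing, so it could not contribute to that review. The trial also has a randomised, blinded placebo arm, which would allow a change in QTc to be set against the change seen after the same surgery and anaesthetic without the study drug. The plan makes no use of that comparison.

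**Working it through.** No figure in the plan depends on this point, so the check consists of setting the relevant statements side by side.

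**1. Every statement about QTc, and whether it gives a time**

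| Place | Content | Time relative to injection |
|---|---|---|
| Section 6, exclusion criterion 6 | QTc above 500 ms excludes | Not stated; pre-dose implied |
| Section 6, extra studies and procedures | QTc on the anaesthesia monitor, strip printed, same exclusion | Not stated; pre-dose implied for the exclusion |
| Section 7, risk item 2 | QTc on the patient monitor, labelled strip saved | Not stated |

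Readings with a stated time relative to the injection: 0 of 3. The data storage section also mentions the strips, but only to say where the paper is kept.

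**2. Order of events.** Section 6 places consent and randomisation before the operating room. The spinal, the surgery and then the injection follow. The QTc reading is described next to intraoperative monitoring. A reading used to decide whether QTc is already prolonged must precede the injection to do its job. That is an inference from its purpose, and it applies to the exclusion reading only.

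**3. Post-dose contacts**

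| Contact | Variables | ECG or QTc |
|---|---|---|
| 1 h | Pain, itching, sedation, nausea/vomiting | None |
| 4-5 h | Same four | None |
| 24 h | Same four | None |

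Scheduled post-dose contacts that include QTc: 0 of 3. A phone contact could not supply one.

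**4. Recording and analysis.** The measurements named for the spreadsheet are the four above; age group, medical conditions and BMI group are to be used for confounding. QTc is in neither list. The secondary analyses in section 5 are sedation, pain and nausea/vomiting. No QTc change or summary by arm is mentioned.

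**5. Comparison with the neighbouring risk.** Sedation, risk item 1, is marked as a study variable and is scheduled three times after dosing. QT prolongation, risk item 2, has no scheduled post-dose measurement.

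**6. What could still reach the safety review.** A clinically evident arrhythmia could, through the adverse event log or as a major reaction. Asymptomatic prolongation could not by any route that the plan describes.

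**The case against.** A reader might infer that the only QTc reading is taken before the injection, and therefore that the trial has no post-dose observation of this toxicity at all. The documents do not support either step as a statement of fact.

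First, no section times the strip. The exclusion rule implies a pre-dose reading, but section 7 gives a QTc reading as the direct response to the drug's risk, without mentioning exclusion or the intraoperative period. A reading at or after the end-of-procedure injection is not scheduled, but it is not ruled out. This changes the description of the defect without removing it: a strip with no known time from dosing cannot be read as evidence about the drug.

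Second, section 7 words the concern as prolongation leading to arrhythmia, and a clinical arrhythmia would be logged and reviewed. This stands. The gap is confined to change without symptoms.

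It can also be said that the trial proposes no QTc claim, so it should not be faulted for being unable to support one. That is fair as far as the objectives go, and it limits the weight of the point. But the protocol itself presents the strip as its answer to a named risk, and it is reasonable to ask that the strip be able to observe that risk.

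Finally, ECG monitoring is documented only during surgery, so a later strip may not be feasible in the PACU. This also stands and limits what the remedy can deliver.

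**Conclusion.** The point holds as a gap in timing and specification. QT prolongation is a named risk; the strip's time relative to the injection is not given; its only described use is to exclude a QTc above 500 ms; and none of the three post-dose contacts, the listed spreadsheet variables or the planned analyses includes QTc. As written, the trial cannot be relied on to yield a QTc comparison between arms.

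The conclusion assumes that the four listed variables are the full content of the post-dose contacts, and that no post-dose strip is taken under a procedure outside this document. If one is intended, the remedy is largely a matter of writing it down.

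The consequence is modest. No efficacy estimate, error rate or power figure is touched. The change is worth making because it costs little and lets the protocol's own QT safeguard observe the risk it is meant to address.

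**What to change.** Reconcile the account of the patient's day and the extra-procedures text in section 6 with risk item 2 in section 7:

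- State that the eligibility strip is taken before dosing, and where it falls relative to randomisation, since randomisation is described before the patient reaches the operating room and the QTc reading alongside intraoperative monitoring.
- In both arms, print a second strip in the same lead at the latest time after the injection at which ECG monitoring is still running. Record its time from Time 0 and add it to the Table of Study Events.
- Enter both QTc values in the de-identified spreadsheet and summarise the change by arm descriptively.

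If no post-dose reading is intended, section 7 should say that the strip is a baseline screen only.

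This adds an observation and no treatment rule. Any QTc threshold, or clinical action on a reading, is for the investigators to decide.

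**Cost.** One extra strip per patient, so 100 strips for the planned 2 × 50 patients, plus spreadsheet columns for the two QTc values and the time of the second strip. The main limitation is that ECG monitoring in the PACU is not documented. If monitoring stops soon after the injection, the second strip reflects only the first minutes after an intramuscular dose and will say little about later change. Recording its time makes that limit visible.
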